#### Clinical Data:

The following non-imaging, clinical data will be obtained:

Expanded Disability Status Scale (EDSS), Timed 25-feet walk (T25W), 9-Hole Peg Test (9HPT), Four component MS Functional Composite (MSFC-4), Symbol-Digit Modality test (SDMT), cognitive and symptom questionnaires, vision testing, Levels of serum biomarkers.

#### Clinical Safety Monitoring:

Safety will be assessed at 0, 3, 6, and 9 months of the study including:

- Pregnancy Testing: All women of childbearing potential will undergo a serum pregnancy test at the screening visit and at each of the following scheduled visits to the hospital. The investigator will also review the contraception status of subjects at each visit.
- Electrocardiogram (ECG): An ECG will be performed either at the screening visit or on day 0 clinical visit and at the end of the study.
- Routine labs: Blood samples will be collected at the screening visit and at each visit time point. Blood samples will be assessed for red blood cell count, hemoglobin, hematocrit, platelets, total white blood cell (WBC) count and WBC differential counts (neutrophils, lymphocytes, basophils, eosinophils, monocytes) as well as for electrolytes (Na, K, Cl, bicarbonate, Ca, Mg, P), random glucose, total protein, blood urea nitrogen, albumin, alkaline phosphatase, ALT, AST, GGT, total bilirubin, conjugated bilirubin, creatinine, amylase, C-Reactive protein.
- Samples for total IgM and IgG levels at baseline, 3, 6 and 9 months
- Patient diary review
- Monthly telephone interview

#### Drug Administration/Dosing:

At the end of the baseline clinic visit, subjects will be instructed by one of the investigators on proper drug administration technique. The first injection of ofatumumab will be performed under the guidance of an appropriately trained healthcare professional in the clinical space at the Brigham MS Center.

We plan to enroll 10 subjects with relapsing MS. All enrolled subjects will receive Ofatumumab 20 mg every 4 weeks, subcutaneously for 9 months during the study. Loading doses will be administered initially at 1, 7 and 14 days. During the study period, all enrolled subjects will undergo five PET scans using [F-18] PBR06 at 0, 5, 28, 90 and 273 days after starting treatment with Ofatumumab.

Ofatumumab (OMB157) is a fully human anti-CD20 monoclonal antibody (mAb) self-administered by a once-monthly subcutaneous injection that is in development for MS. Ofatumumab drug product (also referred as OMB157) is formulated as 20 mg/0.4 mL (50 mg/mL) solution for injection, provided in autoinjectors, for subcutaneous administration. The autoinjectors contain a small overfill to allow for a complete withdrawal of the labeled amount (20 mg) of ofatumumab.

Inclusion Criteria:

- Patients diagnosed with active, relapsing MS course (defined by Lublin 2014 criteria)30. Active disease is defined by at least 1 relapse during the previous 1 year or 2 relapses during the previous 2 years or a positive gadolinium-enhancing MRI scan or MRI scan with new or unequivocally enlarging T2 lesions in previous year.
- Age 18 to 60 years
- EDSS 0 to 5.5
- Subjects either untreated or treated with disease modifying therapies other than those listed in exclusion criteria
- Agree to start treatment with ofatumumab and comply with study procedures for the duration of the study
- No other systemic disease or neurological disorders requiring chronic or acute steroid or other immunosuppressive treatment
- No known hypersensitivity reactions to contrast agents
- None of the exclusion criteria

Exclusion Criteria:

- Subjects suspected of not being able or willing to cooperate or comply with study protocol requirements in the opinion of the investigator.
- Subjects with primary progressive MS (Polman et al 2011)32 or SPMS without disease activity (Lublin et al 2014)30.
- Disease duration of more than 10 years in patients with an EDSS score of 2 or less
- Subjects meeting criteria for neuromyelitis optica (Wingerchuk et al 2015)33.
- Pregnant or nursing (lactating) women, where pregnancy is defined as the state of a female after conception and until the termination of gestation, confirmed by a positive hCG laboratory test.
- Women of child-bearing potential, defined as all women physiologically capable of becoming pregnant, unless they are using highly effective methods of contraception during dosing and for at least 6 months after stopping study medication. Highly effective contraception methods include:
- Total abstinence (when this is in line with the preferred and usual lifestyle of the subject, if accepted by the local regulation). NOTE: Periodic abstinence (e.g., calendar, ovulation, symptothermal, post-ovulation methods) and withdrawal ARE NOT acceptable methods of contraception
- Female sterilization (have had surgical bilateral oophorectomy with or without hysterectomy), total hysterectomy or tubal ligation at least six weeks before taking investigational drug. In case of oophorectomy alone, only when the reproductive status of the woman has been confirmed by follow up hormone level assessment
- For female subjects on the study, the vasectomized male partner should be the sole partner
- Use of oral, (estrogen and progesterone), injected or implanted hormonal methods of contraception or placement of an intrauterine device (IUD) or intrauterine system (IUS) or other forms of hormonal contraception that have comparable efficacy (failure rate <1%), for

example hormone vaginal ring or transdermal hormone contraception. In case of use of oral contraception, women should have been stable on the same pill for a minimum of 3 months before taking investigational drug.

- In case local regulations deviate from the contraception methods listed above, local regulations apply and will be described in the ICF.
- Women are considered post-menopausal and not of child bearing potential if they have had 12 months of natural (spontaneous) amenorrhea with an appropriate clinical profile (e.g. age appropriate, history of vasomotor symptoms) or have had surgical bilateral oophorectomy (with or without hysterectomy), total hysterectomy or tubal ligation at least six weeks. In the case of oophorectomy alone, only when the reproductive status of the woman has been confirmed by follow up hormone level assessment is she considered not of child-bearing potential.
- Subjects with active chronic disease (or stable but treated with immune therapy) of the immune system other than MS (e.g. rheumatoid arthritis, scleroderma, Sjögren's syndrome, Crohn's disease, ulcerative colitis, etc.) or with an immunodeficiency syndrome.
- Subjects with a history of the following:
  - History of any malignancy
  - History of alcohol or drug abuse
  - Primary or secondary immunodeficiency
  - Prior hematopoietic stem cell transplantation
  - History of transplantation or anti-rejection therapy
- Subjects with the following laboratory abnormalities:
  - Abnormal CD19+ B-cell levels at screening (defined as CD19 count <110 cells per microliter)
  - Leukopenia (defined as white blood cell (WBC) count <4000 WBCs per microliter)
  - Lymphopenia (defined as lymphocyte count <1000 lymphocytes per microliter)
  - Hypogammaglobulinemia defined as a level of <500mg/dL will be excluded. All subjects with low serum immunoglobulins should be evaluated by a hematologic expert prior to exclusion in the study.
  - Any abnormality of liver function tests, including ALT/SGPT, AST/SGOT, Alkaline phosphatase, total or direct bilirubin or GGT
- Subjects with active systemic bacterial, viral or fungal infections, or known to have acquired immunodeficiency syndrome (AIDS).
- Subjects with neurological symptoms consistent with PML or confirmed PML.
- Subjects at risk of developing or having reactivation of syphilis or tuberculosis (eg subjects with known exposure to, or history of syphilis, or active or latent tuberculosis, even if previously treated).
- Subjects with low affinity binders (LAB) for TSPO radioligand
- Subjects with abnormal serum creatinine levels (defined as >1.3mg/dL) or Subjects with estimated glomerular filtration rate (eGFR) <30ml/minute
- Patients with history of significant renal disease (dialysis, kidney transplant, single kidney, renal cancer, renal surgery)
- Patient presenting with cardiac disorders defined by at least one of the following conditions:
  - Patient with recent cardiac history (within 6 months) of:
    - Acute coronary syndrome
    - Acute heart failure (class III or IV of the NYHA classification)

- History of significant ventricular arrhythmia (persistent ventricular tachycardia, ventricular fibrillation, resuscitated sudden death)
- Patient with history of cardiac failure class III or IV of the NYHA classification
- Patient with history of severe conduction disorders which are not prevented by permanent pacing (atrio-ventricular block 2 and 3, sinoatrial block)
- Syncope without known etiology within 3 months
- Uncontrolled severe hypertension, according to the judgment of the investigator, or symptomatic hypertension
- Subjects with any contraindications to PET/CT or MRI procedures (e.g. claustrophobia, MRI-incompatible implants or pacemakers, renal failure)
- Subjects with any significant or uncontrolled medical comorbidity
- Subjects with active hepatitis B
- Subjects at risk of hepatitis B reactivation (such as subjects with positive HBsAG or anti-Hepatitis B core antibodies) should be evaluated by a liver disease expert before inclusion, or should be excluded
- Subjects treated with other disease modifying treatments within their respective pre-specified washout periods will be excluded

## **Biostatistical Analysis**

### Study endpoints/variables

The primary endpoint of the study will be the change in PET uptake in the lesional and normal appearing white matter, cortical and subcortical grey matter, and peri-plaque area of chronic lesions in the brain at early and late time-points (5, 28, 90 and 273 days) as compared to baseline.

The secondary endpoints of the study will be the following:

- 1) Association of change in PET uptake in the lesional and normal appearing white matter, cortical and subcortical grey matter, and peri-plaque area of chronic lesions in the brain with changes in the peripheral CD19 counts, serum glial fibrillary acid protein (GFAP) and serum neurofilament light chain measurements at 5, 28, 90 and 273 days as compared to baseline.
- 2) Association of changes in PET uptake in the lesional and normal appearing white matter, cortical and subcortical grey matter, and peri-plaque area of chronic lesions in the brain with MRI and clinical changes at 5, 28, 90 and 273 days as compared to baseline.

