### **Specific Aims:**

Specific Aim 1: To determine the effect of Ofatumumab on microglial activation in MS over 9 months.

Specific Aim 2: To determine the time course of effect of Ofatumumab on microglial activation and its relationship with peripheral B-cell depletion, serum neurofilament light (sNFL) chain and glial-fibrillary acid protein (GFAP) levels and other serum biomarkers

Specific Aim 3: To determine the relationship of PET changes following Ofatumumab initiation with 3T MRI changes and clinical parameters.

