## **Design:**

This is an open-label, observational, prospective, 9-month follow-up study to assess the efficacy of ofatumumab on microglia pathology in patients with MS, as measured by changes in microglial activation in the lesional and non-lesional, normal appearing white matter, cortical and subcortical grey matter, and peri-plaque area of chronic lesions in the brain.

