### Sample size and statistical considerations:

We will recruit 10 subjects, and each subject will undergo PET evaluations at day 0 (baseline), day 5, day 28, day 90 and day 273. The change with time in PET uptake in the lesional and normal appearing white matter, cortical and subcortical grey matter, and peri-plaque area of chronic lesions will be estimated using an analysis of response profiles model including a categorical effect of time and an unstructured covariance matrix for the residuals. This approach allows any change with time and places no structure on the covariance matrix. The primary analysis will be the global comparison across the five time points. If a significant difference among the five time points is observed, we will estimate the

change between day 0 and each of the other measurements, and we will correct for four multiple comparisons using a Bonferroni correction. Since the analysis of response profiles model estimates the parameters using maximum likelihood with the *mixed* command in Stata, this approach will handle missing data that is missing at random. Therefore, subjects who are missing one or more measurement will be included in our analysis. A p-value  $<0.05$  will be considered statistically significant.

In addition to the primary analysis of the change with time, we will also compare the change in PET uptake with the change in other measured variables (MRI, clinical, and immunologic measures). All of the remaining variables will be measured at the same time points as PET uptake (days 0, 5, 28, 90 and 273). First, we will calculate the change from day 0 to each of the other time points for each of the measures, and we will estimate the correlation between the changes using Pearson's correlation coefficient. This analysis will fit several models, but the interpretation of these correlations will be easy to interpret. Second, we will fit a linear mixed model with PET uptake as the outcome and two predictors for each of the other measured variables. In particular, we will include (1) the day 0 measure and (2) the change from day 0 so that we can estimate both the cross-sectional and longitudinal association between the other measured variables and PET. Our focus will be the longitudinal association estimated using the second term. If a subject receives corticosteroids during the study period, we'll account for that in a multivariate analysis by adding it as a covariate.

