#### Sample size calculation:

No prior data regarding effect of Ofatumumab on microglial changes is available at this time. The sample size of 10 is based on the typical number of patients in published PET-MRI studies with the same tracer. With a sample size of 10 subjects, we will be able to estimate the mean change between any pair of time points with a standard error of 0.32 times the standard deviation of the change. Assuming a PET effect size of 1.1 noticeable in intracortical and leukocortical lesions, identified on combination of PET and 3T MRI, a sample size of 10 provides 85% power and alpha-error of less than 5% to detect a treatment response. This means that we will have a reasonable precision for the design of future studies.

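### Five unranked brain regions share the primary endpoint with no rule for which, or how many, must be significant; if any one suffices, the false-positive rate is about 23% with independent regions, 14% at between-region correlation 0.9 and 8% at 0.99

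*Combined protocol and SAP*

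**What the plan says.** The section Study endpoints/variables gives one primary endpoint, "change in PET uptake in the lesional and normal appearing white matter, cortical and subcortical grey matter, and peri-plaque area of chronic lesions", assessed at days 5, 28, 90 and 273 against baseline. That is five regions: white-matter lesions, normal-appearing white matter, cortex, subcortical grey matter and the peri-plaque area. None is put first.

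Other sections do not rank them. Specific Aim 1 names no region ("To determine the effect of Ofatumumab on microglial activation in MS over 9 months"), and Design lists the same areas unranked ("changes in microglial activation in the lesional and non-lesional, normal appearing white matter, cortical and subcortical grey matter" and the peri-plaque area).

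Under Sample size and statistical considerations, the model is described as "including a categorical effect of time and an unstructured covariance matrix for the residuals". It has no region term. "The primary analysis will be the global comparison across the five time points", with p<0.05 as the threshold. If that test is significant, each follow-up visit is compared with day 0, and "we will correct for four multiple comparisons using a Bonferroni correction". No correction is given across regions.

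The Sample size calculation section claims 85% power with an alpha error under 5%: "Assuming a PET effect size of 1.1 noticeable in intracortical and leukocortical lesions".

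**The concern.** The plan controls multiplicity over visits and leaves it open over regions. It does not say how five regional results become one primary conclusion. The success rule could therefore be settled after the results are seen, and a single region with p<0.05 could be reported as a positive primary finding.

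The alpha quoted in the sample size section does not cover this. Its power figure is of the size that one comparison at 0.05 would give. It refers to intracortical and leukocortical lesions, which are not listed as a region in the primary endpoint, so it does not identify a lead region either.

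**Working it through.** **Inputs from the documents.** n = 10, one group; five visits, hence four changes from day 0; five regions; alpha 0.05; Bonferroni over four contrasts; effect size 1.1.

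**Assumptions.** One global test per region (the model has no region term, but the plan does not say this outright); complete data; equal correlation between every pair of regions, varied from 0 to 0.999; compound symmetry over visits, so change scores correlate 0.5.

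**The plan's own figures.**
- Standard error of a mean change: 1/√10 = 0.316 SD, matching the stated 0.32.
- Power for one contrast at effect size 1.1: noncentrality 1.1 × √10 = 3.48. A two-sided paired t-test at 0.05 gives 87.1%. A Wilcoxon signed-rank approximation (efficiency 0.955) gives 85.1%, matching the stated 85%.

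The stated power thus corresponds to a single comparison at 0.05. At the plan's own Bonferroni level, 0.05/4 = 0.0125, the paired t-test has 64.6%.

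**Error over regions, independent case.** 1 − 0.95⁵ = 1 − 0.774 = 0.226.

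**Error over regions, correlated case.** For each region, Hotelling T² on the four change scores gives F = T² × (10 − 4)/(4 × 9) = T²/6, referred to F(4,6) with critical value 4.53. With no true change and 100,000 simulated trials per setting, each region's own error was 0.049 to 0.051. The rates under three possible success rules were:

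| Between-region correlation | Any region | Any region, plus a Bonferroni-significant visit in it | All five |
|---|---|---|---|
| 0 | 0.227 | 0.087 | 0.000 |
| 0.5 | 0.212 | 0.081 | 0.000 |
| 0.8 | 0.168 | 0.064 | 0.002 |
| 0.9 | 0.137 | 0.052 | 0.006 |
| 0.95 | 0.110 | 0.041 | 0.013 |
| 0.98 | 0.087 | 0.033 | 0.022 |
| 0.99 | 0.075 | 0.027 | 0.029 |
| 0.999 | 0.059 | 0.022 | 0.044 |

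The Bonferroni gate is |t| > 3.11 on 9 df. With Holm over the five exact p-values (smallest below 0.01), the any-region rate is 0.050 at correlation 0, 0.034 at 0.9 and 0.018 at 0.99.

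**Dependence on the global test.** The plan's "analysis of response profiles model estimates the parameters using maximum likelihood", and no small-sample method is named. If the Wald statistic is referred to chi-square with 4 df (an assumption), then with complete data W = (10/9)T² = (10/9) × 6F. Rejecting at W > 9.488 means rejecting at F > 9.488 × 0.9/6 = 1.423, and P(F(4,6) > 1.423) = 0.332. One pre-named region would then carry 33% error, and the first Holm step 0.70 at correlation 0 and 0.28 at 0.99.

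**Power cost of Holm.** The first step tests at 0.01 instead of 0.05. The noncentrality is 10 × d′R⁻¹d. With change scores correlating 0.5, R⁻¹ = 2(I − 0.2J), where J is the all-ones matrix. The effect pattern d runs over days 5, 28, 90 and 273:

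| d | Noncentrality | Power at 0.05 | Power at 0.01 | n to match at 0.01 |
|---|---|---|---|---|
| (0, 0, 1.1, 1.1) | 20 × (2.42 − 0.968) = 29.04 | 0.846 | 0.486 | 14 |
| (1.1, 1.1, 1.1, 1.1) | 20 × (4.84 − 3.872) = 19.36 | 0.671 | 0.303 | 14 |
| (0.275, 0.55, 0.825, 1.1) | 20 × (2.26875 − 1.5125) = 15.125 | 0.557 | 0.221 | 15 |

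The loss depends on the assumed correlation. For the first pattern, power falls from 76% to 39% at 0.3 and from 99% to 88% at 0.8. The 85% in the first row is a four-df figure that happens to agree with the plan's 85%; it is a different quantity.

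**The case against.** The strongest reply is that this is a 10-subject, open-label mechanistic study. The sample size section says no prior data exist and ends on precision for designing later studies. No go/no-go decision hangs on the result, and the any-region rule is not written in the plan. Regions scanned in the same subjects are unlikely to be independent, so 23% is an extreme. Any claim about a particular visit must also pass the Bonferroni step, which brings the rate to 9% at correlation 0 and 5% at 0.9. Intracortical lesions lie within cortical grey matter, so the power statement is not wholly detached from the endpoint. The text also speaks of one model and one comparison, so testing per region is an inference.

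Much of this is fair and limits the weight of the point: it matters mainly for how a single significant region is reported. It does not close the gap. The plan declares a primary endpoint, a primary hypothesis test, a 0.05 threshold and power to detect a response, and Design speaks of efficacy. The global test alone is primary, so the Bonferroni step does not protect the primary conclusion. No joint test over regions is described. If the regional p-values are meant to be exploratory, with estimates and confidence intervals as the result, the plan would have to say so and give up the primary-test language.

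**Conclusion.** The concern holds. Five regions carry equal primary status, and no rule combines them. If any one region counts, the false-positive rate is about 23% at between-region correlation 0, 14% at 0.9 and 8% at 0.99, and it nears 5% only as the correlation nears 1. If all five must be significant, it stays below 5%. The plan does not choose between these rules.

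The figures rest on one global test per region, an exact small-sample test, complete data and assumed correlations. They are lower than maximum likelihood with a chi-square reference would give. This should be corrected before analysis. It does not call the data collection into question.

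**What to change.** State the success rule in the SAP before the data are analysed.

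- **Preferred:** name one of the five regions as primary, test its global time effect at 0.05, and make the other four secondary with Holm.
- **Alternative:** keep all five as primary and apply Holm to the five global p-values, so that the smallest must be below 0.05/5 = 0.01.

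Under either option, run the day-0 contrasts only in regions that pass, at the plan's 0.05/4. Say that this level controls error within a region and not over all 5 × 4 = 20 contrasts. Also specify a global test that is valid at this sample size, for example REML with Kenward-Roger degrees of freedom, or Hotelling T² for complete data. Without that, neither option holds the error at 5%.

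The change is SAP wording and needs no new data. The preferred option costs four regions their primary status. The alternative costs power: in the illustrations above, 85% falls to 49%, 67% to 30% and 56% to 22%, and about 14 to 15 subjects would be needed to recover it. The loss is smaller if several regions respond, because later Holm steps are less strict.

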### Sample size and statistical considerations:

We will recruit 10 subjects, and each subject will undergo PET evaluations at day 0 (baseline), day 5, day 28, day 90 and day 273. The change with time in PET uptake in the lesional and normal appearing white matter, cortical and subcortical grey matter, and peri-plaque area of chronic lesions will be estimated using an analysis of response profiles model including a categorical effect of time and an unstructured covariance matrix for the residuals. This approach allows any change with time and places no structure on the covariance matrix. The primary analysis will be the global comparison across the five time points. If a significant difference among the five time points is observed, we will estimate the

change between day 0 and each of the other measurements, and we will correct for four multiple comparisons using a Bonferroni correction. Since the analysis of response profiles model estimates the parameters using maximum likelihood with the *mixed* command in Stata, this approach will handle missing data that is missing at random. Therefore, subjects who are missing one or more measurement will be included in our analysis. A p-value  $<0.05$  will be considered statistically significant.

In addition to the primary analysis of the change with time, we will also compare the change in PET uptake with the change in other measured variables (MRI, clinical, and immunologic measures). All of the remaining variables will be measured at the same time points as PET uptake (days 0, 5, 28, 90 and 273). First, we will calculate the change from day 0 to each of the other time points for each of the measures, and we will estimate the correlation between the changes using Pearson's correlation coefficient. This analysis will fit several models, but the interpretation of these correlations will be easy to interpret. Second, we will fit a linear mixed model with PET uptake as the outcome and two predictors for each of the other measured variables. In particular, we will include (1) the day 0 measure and (2) the change from day 0 so that we can estimate both the cross-sectional and longitudinal association between the other measured variables and PET. Our focus will be the longitudinal association estimated using the second term. If a subject receives corticosteroids during the study period, we'll account for that in a multivariate analysis by adding it as a covariate.

Paired t-test and repeated measures ANOVA analyses will be performed to assess differences in PET measures over time. Correlation analyses will be performed between PET and MRI measures and clinical variables. We will also look for correlations between changes in PET uptake and peripheral CD19 counts at various time points of the study.

Statistical analyses will be performed using Stata version 16 (StataCorp, College Station, Texas, USA).

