#### *Role of microglia in MS:*

Multiple sclerosis (MS) is primarily a demyelinating disease of the central nervous system (CNS), but many patients also undergo progressive atrophy, especially in the gray matter (GM). GM atrophy plays a particularly prominent role in cognitive and physical decline in MS. White matter (WM) demyelination is also correlated with cognitive and physical impairment, albeit GM pathology accounts for the most variance in predicting cognitive and physical impairment.

Both neuroinflammation and neurodegeneration occur during all stages of MS. Axonal loss underlies especially the transition from relapsing to progressive MS, but neurodegeneration with axonal transections is known to be present already early in the disease. By studying progressive MS, one may thus gain important insights about the degenerative component of MS present in all stages of the disease.

Microglia are myeloid cells of the CNS are derived from early embryonic erythromyeloid progenitor cells and have migrated into the developing nervous tissue, where they have begun the maturation process into brain-resident microglial cells. Microglia constitute approximately 10% of the total cell population in a human brain. The key tasks performed by microglia include phagocytosis of extracellular debris, antigen presentation to host immune cells, and secretion of inflammatory mediators.

In the early phase of MS, microglial activation promotes the recruitment of naïve T cells, which are activated in the periphery by dendritic cells functioning as antigen-presenting cells. Microglia also act as antigen-presenting cells, re-stimulating the auto-reactive memory-T-cells invading through the blood-brain barrier (BBB) into the CNS. This is considered a key event in maintaining the chronic inflammation in the CNS. In active WM lesions, there is a profound infiltration of activated microglia and blood-borne macrophages throughout the lesion, whereas in slowly expanding (smoldering) or chronic active lesions, the microglia and macrophages are concentrated as a dense rim

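### The 5% error rate of the single-arm primary test refers to no change in uptake over time, so the plan should not present a rejection as ofatumumab efficacy or a treatment response

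*Combined protocol and SAP*

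**What the plan says.** **The question.** Specific Aim 1 is "To determine the effect of Ofatumumab on microglial activation in MS over 9 months". The Design section describes an open-label, observational study "to assess the efficacy of ofatumumab on microglia pathology in patients with MS".

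**The design.** Under Drug Administration/Dosing, all 10 subjects are treated. Under PET Scanning, there is one scan before treatment and four after it (about days 5, 28, 90 and 273). The plan has no comparator, untreated run-in or repeat baseline.

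**The test.** Under Sample size and statistical considerations, the model has a categorical time effect, and "The primary analysis will be the global comparison across the five time points". If it is significant, changes from day 0 follow with a Bonferroni correction for four comparisons. Corticosteroid use is the only other cause of change that the plan adjusts for.

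**The claim attached to the test.** Under Sample size calculation, "a sample size of 10 provides 85% power and alpha-error of less than 5% to detect a treatment response".

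**Entry and regions.** The inclusion criteria require active disease, shown by relapse history or by "a positive gadolinium-enhancing MRI scan or MRI scan with new or unequivocally enlarging T2 lesions in previous year". The endpoint is "change in PET uptake in the lesional and normal appearing white matter, cortical and subcortical grey matter, and peri-plaque area of chronic lesions". The word chronic qualifies only the peri-plaque area. The background section on microglia says: "In active WM lesions, there is a profound infiltration of activated microglia and blood-borne macrophages throughout the lesion".

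**The concern.** The test and the claim have different nulls. The test asks whether mean uptake is the same at five visits. The claim is that the drug has an effect. The two coincide only if uptake would stay flat without the drug, and the plan neither states nor supports that.

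The plan's own text gives one concrete way in which the assumption could fail. Subjects are chosen for recent disease activity, active lesions are rich in the cells the tracer is meant to show, and nothing keeps lesions enhancing at day 0 out of the lesional white matter region. If such lesions are present at baseline and settle over 273 days, lesional uptake falls with no drug effect, and the plan's wording would call that a treatment response. The plan also says the results will inform the design of future studies, so a mislabelled effect size would be carried forward.

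**Working it through.** **1. The plan's own figures.** Inputs from Sample size calculation: n = 10, standardised effect 1.1, alpha 5%, power 85%, SE of 0.32 SD of change.

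- SE: 1/√10 = 0.316, which agrees with 0.32.
- Power, one-sample (paired) t-test, two-sided 0.05, 9 df, noncentrality 1.1 × √10 = 3.48: 87.1%. With the Wilcoxon signed-rank efficiency (effective n = 10 × 3/π = 9.55): 85.1%.
- A two-group comparison does not give 85%: t-based power is 33% with 5 per arm and 64% with 10 per arm.

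So the 85% is power to detect a within-subject change from any cause. With no drug effect and a natural change of 1.1 SD, the same calculation gives the same 85–87% chance of significance.

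**2. Rejection rate with no drug effect and an assumed natural change.** The documents give no natural-course figure, so this is a range. Assume a mean change of D × (0, 0.5, 1, 1) at days 5, 28, 90 and 273, in SD of change, with equal correlation ρ between changes. An exact global test (Hotelling T²) is used so that the small-sample behaviour of the maximum-likelihood test plays no part.

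- F = T² × (10 − 4)/(4 × 9), on 4 and 6 df; critical value 4.53.
- Noncentrality λ = 10 × D² × q, where q = [2.25 − 6.25ρ/(1 + 3ρ)]/(1 − ρ). This gives q = 2.00 at ρ = 0.5 and 2.80 at ρ = 0.7.

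| D | λ (ρ = 0.5 / 0.7) | Global test rejects | One paired t at 0.05 | One paired t at 0.0125 |
|---|---|---|---|---|
| 0.25 | 1.25 / 1.75 | 8.5% / 10.0% | 11% | 3% |
| 0.50 | 5.00 / 6.99 | 21% / 28% | 29% | 12% |
| 0.75 | 11.25 / 15.7 | 43% / 57% | 56% | 30% |

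The last column is the Bonferroni level, 0.05/4.

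**3. The same test, driven by enhancing lesions.** Simulation with 40,000 trials per cell and no drug effect. Assumptions: a share of subjects has excess lesional uptake at day 0, of which 90% remains at day 5, 50% at day 28 and none at days 90 and 273. Independent per-scan retest error is added. None of these inputs is in the documents.

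| Day-0 excess | Retest SD | 30% of subjects | 50% | 80% |
|---|---|---|---|---|
| 6% | 5% | 7.4% | 12.2% | 28.6% |
| 6% | 8% | 5.9% | 8.1% | 14.0% |
| 6% | 12% | 5.4% | 6.7% | 9.0% |
| 3% | 5% | 5.5% | 7.0% | 10.7% |
| 3% | 8% | 5.6% | 5.6% | 6.9% |
| 3% | 12% | 5.0% | 5.4% | 6.0% |

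If few subjects enhance at day 0, the rate stays close to 5%. It rises materially only when most subjects enhance and the scan is precise.

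**The case against.** The strongest reply is that this is an openly single-arm pilot. It calls itself observational, defines its endpoint as change from baseline, frames its sample size as precision for later studies, relates PET change to MRI change at every visit, and adjusts for corticosteroids. All of that is true. It makes the analysis itself legitimate, but it does not remove the efficacy and treatment-response wording or give the stated alpha a meaning it lacks.

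Several further objections stand and limit the point:

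- The activity criterion looks back one year, or two years for the two-relapse route, and can be met by relapse or T2 change alone. An enhancing lesion at day 0 is not required.
- That enhancing lesions enter the lesional region is inferred from the absence of an exclusion. The plan does not define the lesion mask.
- The mechanism bears mainly on lesional white matter. Normal-appearing white matter, grey matter and the peri-plaque area of chronic lesions are largely untouched by it, although the general single-arm limitation applies to them too.
- The global test is non-directional, and the follow-up comparisons are Bonferroni-corrected, which lowers their rejection rates.

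A reader might infer that the bias runs in the drug's favour and that the effect size passed on will be too large. The documents do not support that. Patients with active disease can form new lesions over nine months, which would raise uptake and could hide a drug effect. The background section also describes microglial activation as chronic and self-propagating, which does not imply a fall.

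**Conclusion.** The point holds as a mismatch between test and claim. The alpha below 5% and the 85% power apply to within-subject change over time, not to a drug effect against no treatment. This follows from the design and needs no assumption about the natural course.

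The lesion mechanism is a plausible route to misattribution in one region, of unknown size and net direction. Under the assumed inputs with no drug effect, the exact global test rejects in about 5–7% of trials when 30% of subjects have enhancing lesions and in 6% to about 29% when 80% do. A natural change of 0.5 SD gives 21–28%. These figures rest on the assumed excess, decay, retest SD and correlation.

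It would go too far to conclude that acute lesions are known to be in the lesional region, that the primary test is compromised in every region, or that enhancing lesions must be dropped from the primary region. Dropping them would change the target and could remove tissue where a drug effect is plausible.

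**What to change.** 1. **Wording.** In Design and in Sample size calculation, replace the efficacy and treatment-response language with change in PET uptake after starting ofatumumab. State that the alpha and the 85% power refer to within-subject change over time, not to a drug effect against no treatment.
2. **Parallel analysis.** In Study endpoints/variables and in Sample size and statistical considerations, keep the lesional white matter region as planned. Pre-specify a parallel analysis limited to lesions not gadolinium-enhancing on the day-0 MRI. Apply the same day-0 lesion mask at all five visits, so that lesions appearing later do not enter it. Report day-0 enhancing lesions separately.
3. **Reading rule.** State in advance that a fall confined to day-0 enhancing lesions will not be attributed to ofatumumab.

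The cost is text and one extra mask. Contrast MRI is already planned at every visit, so no new scans, visits or subjects are needed. The downsides are a noisier estimate from less lesion tissue and a weaker headline claim. Natural change in recent lesions that no longer enhance is reduced, not removed, and the study remains uncontrolled.
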